Patient-delivered treatment holds great promise; however, there is still much to learn. To date, all patient-delivered interventions have used a hybrid approach in which targeted patients receive care from fellow patients *and* professionals. No study has ever trained patient providers to execute all treatment components. Moreover, a recent Cochrane review calls for 1) studies that investigate whether patient-provided care is naturally sustained once formal treatment ends, 2) more evidence-based patient training, and 3) rigorous efficacy trials.^[14] Lastly, qualitative data suggest that, given their shared experience, patients provide one another with a unique sense of empathy and inspiration, not duplicated by professionals;^[15] however, the unique mechanisms by which patients may promote health behavior change have never been examined. The proposed project will fill these gaps. We will 1) eliminate professional providers from our patient-delivered intervention, 2) examine the extent to which patient-provided treatment is naturally sustained once formal treatment ends, 3) provide patients with evidence-based training in weight management and autonomy support (a type of support consistently linked to maintenance success^[16]), and 4) examine the mechanisms (e.g., empathy, inspiration) by which patient providers impact outcomes. Regarding the latter, these 2 types of patient providers have potentially unique strengths (due to their success, mentors may provide inspiration; given they are actively changing behavior, peers may provide empathy), thus, we will also capitalize on the unique strengths of each and involve both types of patient providers in one treatment, which has not been done.

Consistent with contemporary weight loss maintenance trial designs,^[17] this study involves two phases: a weight loss induction phase and a maintenance phase. During Phase I (weight loss) individuals will complete a 16-week Internet weight loss program. Those who achieve a $\geq 5\%$ ^[1] weight loss will be invited

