to participate in Phase II, the actual maintenance trial. The maintenance trial will be a head-to-head comparison of current best practice for maintenance vs. patient-delivered treatment. Specifically, Phase II participants will be randomized to either best practice (Standard) or a novel patient-to-patient intervention (P2P). Both treatments will be 18 months. Standard will include 24 group sessions delivered by a professional that taper over time (consistent with current best practice^[4]). P2P will involve 7 group sessions, all delivered by a trained mentor (successful weight loser), followed by peer patient-to-patient coaching via email or text. Because peers are uniquely capable of providing *ongoing* contact at *low cost*, peer coaching will be weekly. We hypothesize that P2P will yield significantly better maintenance because it involves (a) weekly (instead of tapered) contact (b) potentially powerful components unique to patient-provided treatment (empathy, hope, inspiration^[15]), and (c) autonomy support (evidence-based support associated with maintenance success^[16]). Detailed hypotheses are below.

Primary hypothesis: P2P will yield significantly less weight regain compared to Standard at 18-months.

Secondary hypothesis: P2P will have better CVD risk profiles (blood pressure) compared to Standard at 18-months.

Exploratory aims:

1. Examine whether components unique to patient-to-patient care (empathy, inspiration, hope, autonomy support) mediate P2P vs. Standard weight outcomes at month 18.
2. Explore the cost-effectiveness of P2P vs. Standard at 18-months.
3. Investigate the sustainability of patient coaching during the no treatment follow-up period (18-24 months) by examining (a) the extent to which patients continue to coach one another and (b) differences in P2P vs. Standard on the following outcomes: weight, CVD, empathy, hope, inspiration, and autonomy support.

Design, Procedures, Materials, and Methods.

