Empathy, Compassion, Hope, and Inspiration. For the first time, mediators thought to be specific to patient-provided care will be assessed. Validated measures will be used. Empathy will be assessed with Jefferson's Patient Perception of Empathy Scale.^[38] Compassion will be assessed with the Compassion Scale.^[39] Hope and inspiration will be assessed with two measures of these constructs validated for use with patients.^[40, 41] All participants will complete these measures keeping in mind important others in their life (partner, family, friends). P2P participants will also answer these questions keeping in mind their relationship with their peer partner. Standard participants will answer these questions keeping in mind their relationship with their group leader.

Autonomy support. Autonomy support for weight control will be assessed with the validated Important Other Climate Questionnaire.^[42]

Other possible mediators. Adherence will be assessed by examining frequency of self-weighing using a validated measure.^[55] General weight-related social support will be assessed using the validated Social Support for Healthy Behaviors Questionnaire.^[56] Finally, we will assess “non-specific” factors (task and bond alliance) between participants and providers with the validated Working Alliance Inventory.^[54]

Cost-effectiveness, diet, activity, session attendance, and peer patient e-coaching.

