Secondary hypotheses. Analyses will test differences in P2P vs Standard on cardiovascular outcomes (blood pressure) at 18 months using linear mixed models identical to the primary analysis.

Exploratory hypothesis 1. We will explore mediation effects for each of our proposed mediators (e.g., empathy, compassion, hope, inspiration) on weight change from baseline to month 18 using the Mediation package in R.^[75, 76] General or generalized mixed effects models will be created for the indirect and total effects to determine the proportion of the mediation effect. A causal inference approach was selected over multiple regression because of the dyadic and multilevel nature of our models, the possible feedback between dependent and mediating variables, and its ability to relax identification assumptions when needed.^[77, 78]

Exploratory hypothesis 2. Cost-effectiveness of the two interventions will be examined. Data from our cost measures, utility measure, and trial results (kg of weight change from baseline to month 18) will be used. Multi-way sensitivity analyses will be conducted to show how different variables interact. P2P participants will be sampled in pairs, so as to maintain their within-pair correlation structure. Univariate sensitivity analyses will be performed on all variables and assumptions used in the analyses. A Monte Carlo simulation will be used to vary all of the input parameters over their relevant ranges simultaneously

and to estimate the 95% confidence intervals for incremental cost-effectiveness analyses. The cost-utility analysis will use similar methods to estimate the incremental cost-utility of Standard and P2P at 18-months.

Exploratory hypothesis 3. To explore the sustainability of peer patient e-coaching, we will compare the number of completed coaching weeks, number of overall exchanges, and frequency of exchanges per week from months 18-24 vs. months 12-18 using dyadic analysis similar to Aim 1. Also, to examine if P2P and Standard differ in 24 month weight, CVD, and process outcomes (e.g., empathy, hope, inspiration, autonomy support), analyses similar to the primary aim will be conducted.

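### Exploratory hypothesis 1 appears to test related mediators one at a time as proportions of the total effect; if they are correlated the shares overlap, and the proportion is unusable when the arm difference is small

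*Combined protocol and SAP*

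**What the plan says.** The combined protocol and SAP, under Analyses, Exploratory hypothesis 1, states: "We will explore mediation effects for each of our proposed mediators". It gives empathy, compassion, hope and inspiration as examples, and the outcome is weight change from baseline to month 18. The summary follows: "General or generalized mixed effects models will be created for the indirect and total effects to determine the proportion of the mediation effect". The work is to be done with the R Mediation package. The reasons given for a causal approach are the dyadic and multilevel data, possible feedback between mediator and outcome, and flexibility on identification assumptions. Dependence among the mediators themselves is not mentioned.

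The corresponding entry under Exploratory aims reads: "Examine whether components unique to patient-to-patient care (empathy, inspiration, hope, autonomy support) mediate P2P vs. Standard weight outcomes at month 18". Compassion is added in the Mediators section and in the analysis text, which makes five constructs. The Mediators section then lists self-weighing, weight-related social support and working alliance as further candidates, so there are about eight in all.

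On measurement, every participant completes the empathy, compassion, hope and inspiration scales about important others. In addition, "P2P participants will also answer these questions keeping in mind their relationship with their peer partner", while Standard participants do so about their group leader. The Phase II assessment schedule puts all mediators at the same visits.

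The documents describe no joint model, no treatment of correlation or causal order among mediators, no interval for the proportion and no condition for leaving it out.

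**The concern.** Two separate weaknesses meet in this analysis.

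The first is overlap. A single-mediator model attributes to the tested mediator its own effect plus part of the effect of any omitted mediator that is correlated with it given arm. Correlation is likely here: the same person rates the constructs at the same visits, several scales refer to the same people, and the P2P training teaches empathy as part of autonomy support. A construct with no effect on weight could then be reported as a mediator, and a set of shares could be read as a breakdown of the effect when it is not one.

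The second is the ratio. The proportion mediated has the P2P-Standard difference as its denominator. If the observed difference is well below the planned one, the ratio can take almost any value.

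What is at stake is the interpretation of the mechanism findings. The test of P2P against Standard at month 18 is not.

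**Working it through.** **Inputs from the documents (Power paragraph).** Difference 2.5 kg; SD 6 kg; 110 Standard and 124 P2P (62 dyads); ICC 0.20; stated power 85%. Two-sided alpha of 0.05 is assumed, because none is stated.

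**Reproducing the plan's figure.** The effective P2P size is 124 / (1 + 0.20) = 103.3. The standard error (SE) of the total effect is 6 × √(1/110 + 1/103.3) = 0.82 kg. Power is Φ(2.5/0.822 − 1.96) = 0.86, in line with the stated 85%. The 0.82 kg is therefore a fair precision for the denominator of the proportion.

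**Overlap.** Assume K standardised mediators with equal arm effects, equal effects on weight and a common within-arm correlation r. A mediator with true share s then shows, when tested alone, s × (1 + (K − 1)r). With K = 5 and s = 10% (true joint share 50%):

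| r | Each tested alone | Sum of shares |
|---|---|---|
| 0 | 10% | 50% |
| 0.5 | 10% × 3.0 = 30% | 150% |
| 0.6 | 10% × 3.4 = 34% | 170% |
| 0.7 | 10% × 3.8 = 38% | 190% |

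If J is the true joint share, the sum passes 100% once r exceeds (1/J − 1)/(K − 1). For J = 50% and K = 5 that is 1/4 = 0.25.

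**Inert mediators.** A participant-level simulation used the plan's arm sizes, ICC and SD. One of four mediators was active with a 60% share (1.5 kg of 2.5 kg), and r was 0.5. Tested alone, each of the three inert mediators showed about 0.75 kg, or 0.75/2.5 = 30%. In a joint model each showed about 0 and the active one kept about 1.5 kg.

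**Precision of the proportion.** Assume a true share of 30% and an indirect-effect SE of 0.3 kg, with the total-effect SE at 0.82 kg. The indirect effect is part of the total effect, so the two estimates need not be independent. Both cases are shown as the central 95% range of the estimated proportion:

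| True total effect | Independent estimates | Correlation 0.5 (assumed) |
|---|---|---|
| 2.5 kg | about 6% to 95% | about 9% to 67% |
| 1.25 kg | about −190% to 290% | about −100% to 190% |

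At 2.5 kg, restricting to draws with a significant total effect (86% of them) narrows the independent case to about 6-61%. At 1.25 kg only about 33% of trials would reach significance.

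**Cost of a joint model.** For five mediators the variance inflation factor is 1 / (1 − 4r²/(1 + 3r)), which is 1.67, 2.06 and 2.72 at r = 0.5, 0.6 and 0.7. The square roots, 1.29, 1.43 and 1.65, are the factors by which component intervals widen.

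**The case against.** The best defence has four parts.

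*A single-mediator model is not wrong merely because other mediators act on weight.* This stands. A reader might infer that any other active mediator invalidates it, but the formula above returns the true share at r = 0 with all five active. Bias needs dependence between mediators given arm, and the documents give no correlation. Part of the case for correlation is itself inferred: autonomy support has its own instrument, and no partner or leader referent is stated for it.

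*The aim asks whether these components mediate, not how to divide the effect among them.* This also stands. A reader might take the introduction's remark that "the unique mechanisms by which patients may promote health behavior change have never been examined" as a promise to isolate each construct's own contribution. In context, unique means particular to patients as opposed to professionals. No section proposes to add or rank shares. Even so, a false positive for an inert mediator bears directly on the question of whether it mediates.

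*A joint model is not uniformly better.* Correct. If empathy raises hope and hope affects weight, the path through hope legitimately belongs to empathy, and a joint model removes it from empathy's component. That argues for adding a joint model, not for replacing the single-mediator ones.

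*The analysis is exploratory, and indirect effects in kg will be available anyway.* True, and this limits the weight of the point. But the proportion is the only summary that the plan names, and it carries no safeguard.

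**Conclusion.** The point holds as an inexpensive improvement to an exploratory aim. One-at-a-time analysis is the natural reading of the text, though the text does not say so outright. Under that reading, correlated mediators share credit: 30-38% shown for a true 10% in the five-mediator illustration, and no distortion without correlation. The proportion is wide at the planned 2.5 kg and uninterpretable at about half of that.

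The 0.82 kg SE follows from the plan's inputs with two-sided alpha of 0.05 assumed. The mediator correlations, the equal effects, the 0.3 kg indirect-effect SE and the correlation of 0.5 between the two estimates are all assumptions. The figures show the scale of the problem and do not predict this trial's results.

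A reader might go further and conclude that the planned mediation models are invalid, or that the trial's efficacy conclusions are at risk. The documents support neither: the single-mediator models remain informative with the right caveat, and the primary and secondary tests do not depend on them.

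**What to change.** In Exploratory hypothesis 1:

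- State that the single-mediator models will be fitted, and add one outcome model containing the listed mediators together.
- From the joint model, report the joint indirect effect and each component's effect given the others, in kg with 95% intervals.
- State that the separate shares overlap and must not be summed, and that the joint model leaves out an upstream mediator's path through downstream ones.
- Report a proportion mediated, with its interval, only when the 95% interval for the total effect excludes zero.

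No new data are needed. The cost is analysis wording and code, plus component intervals about 1.3 to 1.6 times wider in the joint model at correlations of 0.5 to 0.7. That width shows how far the data can separate the constructs.

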Overview of the two weight loss maintenance interventions. Both Standard and P2P participants will receive an 18-month weight loss maintenance program and evidence-based weight loss maintenance strategies. The Standard arm will be consistent with current best practice for long-term weight control; it will involve 24 in-person sessions delivered by a professional. In contrast, P2P will be a new treatment approach in which intervention providers are patients (mentors and peers), there are substantially fewer sessions compared to traditional care (7 vs. 24), and peer patient dyads engage in weekly e-coaching. The number of sessions in P2P will be reduced for the following reasons: (1) there is strong evidence that regular in-person weight control sessions are not well attended long-term (i.e., 15-36% attendance at month 24),^[5, 44] thus, transitioning from in-person treatment to peer e-coaching may reduce in-person treatment barriers (time, transportation, childcare) and enhance engagement relative to traditional approaches; (2) minimal in-person contact with patient e-coaching has demonstrated high engagement and excellent weight loss outcomes in our previous trials, and (3) the reduced contact schedule enhances dissemination potential by minimizing costs (no need for rooms, rent, utilities, etc.). Thus, we believe the schedule is reasonable / appropriately justified. Mentor patients (i.e., successful weight losers) will deliver the 7 in-person sessions. During these sessions, peer patient dyads (participant pairs) will engage in relationship building activities with one another and be trained in how to provide evidence-based e-coaching, including weight management strategies and autonomy support. Then, from months 4-18, P2P participants will have no in person treatment; instead, during this time, peer patient dyads will engage in weekly evidence-based e-coaching. Mentor patients will monitor e-coaching and provide corrective suggestions, if necessary. In addition, mentors will e-mail maintenance intervention materials to participants. These materials will involve evidence-based weight control strategies plus relevant patient-to-patient peer activities that promote autonomy support. P2P participants will also have the option of participating in a secret Facebook group that includes their mentors and other group members. Being involved in a secret group means that the public is unable to “see” the group and only the study team can invite users (mentors and participants). Please see below for Standard and P2P intervention details and the appendix for additional intervention information.

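### The cost-effectiveness 95% confidence intervals come from a Monte Carlo over unspecified ranges, with no stated link to the planned pair sampling, so 95% coverage is not assured

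*Combined protocol and SAP*

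**What the plan says.** The method is in the combined protocol and SAP, Analyses, Exploratory hypothesis 2. The effect measure is weight change: "trial results (kg of weight change from baseline to month 18) will be used". One sentence describes the interval. The simulation is meant "to estimate the 95% confidence intervals for incremental cost-effectiveness analyses". Its method is given as follows: "A Monte Carlo simulation will be used to vary all of the input parameters over their relevant ranges simultaneously". No range, distribution or source for a range is given.

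Two other sentences in that paragraph bear on the point. One concerns sampling: "P2P participants will be sampled in pairs, so as to maintain their within-pair correlation structure". It does not say what the sampling is for, and no matching sentence covers Standard. The other plans one-at-a-time sensitivity analyses: "Univariate sensitivity analyses will be performed on all variables and assumptions used in the analyses". The cost-utility analysis inherits the approach: "The cost-utility analysis will use similar methods to estimate the incremental cost-utility of Standard and P2P at 18-months".

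The Cost-effectiveness assessment section takes payer, participant and societal perspectives. Payer labor is priced at market values and rent at local costs. Participants' costs come from questionnaires and include time spent on sessions, coaching and travel. The Overview of the two weight loss maintenance interventions expects lower delivery cost for P2P: "the reduced contact schedule enhances dissemination potential by minimizing costs". The introduction hypothesizes better maintenance with P2P. The plan names no net-benefit measure, willingness-to-pay value, cost-effectiveness plane or rule for reporting dominance.

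**The concern.** A confidence interval has its stated coverage because its width follows from sampling error. An interval obtained by moving inputs across ranges has the width that the ranges give it. The two agree only if the ranges and distributions are set to reproduce sampling error, including the correlation between a person's cost and weight change. The plan does not say that they will be.

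The second issue is the summary measure. With P2P hypothesized to be better and expected to be cheaper to deliver, a cost-per-kg ratio would be negative. Negative ratios have no useful ordering, and their interval breaks down when the effect may be close to zero.

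At stake is whether readers of the cost-effectiveness and cost-utility results can take a reported 95% interval at face value, and whether they can interpret it if the weight effect turns out smaller than planned.

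**Working it through.** **Inputs from the plan (Power section).** Difference 2.5 kg; SD 6 kg; dyad ICC 0.20; 110 in Standard; 124 in P2P (62 dyads); stated power 85%. Alpha is not stated, so two-sided 0.05 is assumed.

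**Assumed inputs (the plan gives none).** Uniform ranges around 2.5 kg; a P2P saving of $300 with SE $60; independent normal errors for cost and effect; willingness to pay of $100 per kg.

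**1. Reproduce the plan's power.** The design effect for pairs is 1 + 0.20 = 1.20, so the effective P2P size is 124 / 1.20 = 103.3. SE = 6 × √(1/110 + 1/103.3) = 0.822 kg. Power = Φ(2.5/0.822 − 1.96) = Φ(1.08) = 86.0%, which agrees with the stated 85% to within rounding. The SE can be used.

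**2. Sampling-based interval for the effect.** Half-width = 1.96 × 0.822 = 1.61 kg, or 0.89 to 4.11 kg around 2.5 kg. In a simulation of 1,000 trials at these design values, a bootstrap resampling dyads in P2P and individuals in Standard covered the true difference 94.3% of the time.

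**3. Range-based interval for the effect.** If the input is uniform over ±h, the central 95% has half-width 0.95h. If that interval is centred on the estimate, its coverage of the true difference is 2Φ(0.95h/0.822) − 1.

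| Assumed range around 2.5 kg | h (kg) | 95% half-width (kg) | Against 1.61 kg | Coverage |
|---|---|---|---|---|
| ±10% | 0.25 | 0.24 | 85% narrower | 22.7% |
| ±25% | 0.625 | 0.59 | 63% narrower | 53.0% |
| ±50% | 1.25 | 1.19 | 26% narrower | 85.1% |
| ±75% | 1.875 | 1.78 | 11% wider | 97.0% |
| ±100% | 2.5 | 2.38 | 47% wider | 99.6% |

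Neither the direction nor the size of the error is fixed by the text.

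**4. Behaviour of a cost-per-kg ratio.** Three results share the same ratio of −$120 per kg: $300 cheaper and 2.5 kg better (−300/2.5), $600 cheaper and 5 kg better (−600/5), and $300 dearer and 2.5 kg worse (300/−2.5). Net benefit, 100 × effect − cost, separates them: +$550, +$1,100 and −$550.

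Percentile limits of cost/effect, from random draws with cost difference −$300 (SE $60) and effect SE 0.822 kg:

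| True effect | Draws cheaper and better | Ratio, 95% limits ($/kg) | Net benefit at $100/kg, 95% limits |
|---|---|---|---|
| 2.5 kg | 99.9% | about −346 to −59 | $351 to $749 |
| 1 kg | 88.8% | about −3,000 to +2,500 | $201 to $599 |

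The net-benefit limits are mean ± 1.96 × √(60² + (100 × 0.822)²), which is mean ± $199, with means of $550 and $400. At 1 kg, about 11% of draws are cheaper but worse. Those give positive ratios, so the limits mix two quadrants.

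**The case against.** A reader might infer that the ranges will be picked by hand, that sampling error is ignored, and that the result is therefore not a confidence interval at all. The documents do not establish this. Ranges described only as relevant could be set from sampling distributions, and the same paragraph plans to sample P2P in pairs, which points toward participant-level resampling. If that sampling feeds the interval, coverage can be close to nominal, as step 2 shows. What remains is that the paragraph does not make the connection and is silent on Standard.

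A reader might also infer that the interval must be too narrow. It need not be: the assumed ranges of ±75% and ±100% overshoot.

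On the ratio, the plan never names one, and at its own 2.5 kg the limits stay in one quadrant and read as dominance, for which no ranking is needed. Both objections stand. The difficulty is confined to smaller true effects and to a reading that is natural but unstated. Nor does the plan say that P2P will cost less from every perspective. The expected saving concerns delivery, while weekly coaching time is charged to participants, so the sign of the societal cost difference is open.

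Finally, labor values and rent are unit costs with no participant sampling error. Varying them over ranges is legitimate, and a participant bootstrap alone would miss that uncertainty. This stands too, and the range-based simulation should be kept for those inputs.

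**Conclusion.** The point holds in limited form. The plan attaches a 95% confidence label to a procedure whose width is not determined by anything stated. At the design values, the 95% half-width for the effect input could be anywhere from 0.24 to 2.38 kg under the assumed ranges, against 1.61 kg from sampling error. The cost-utility analysis has the same gap. If a cost-per-kg ratio is reported, its interval is usable at 2.5 kg but not at 1 kg, under the assumed $300 saving and SE $60.

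The kg figures rest on the plan's SD, ICC and sample sizes plus assumed uniform ranges. Every dollar figure is illustrative. Two missing facts would settle the matter: what the ranges are, and how pair sampling enters the interval. This is a minor point on an exploratory aim and does not touch the 18-month weight comparison.

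**What to change.** Amend Exploratory hypothesis 2 as follows:

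- Obtain the 95% intervals by a stratified bootstrap: dyads in P2P, individuals in Standard, with each person's cost and effect (or utility) drawn together.
- Apply it to incremental cost, incremental effect and incremental net benefit over a stated range of willingness-to-pay values, separately for each cost perspective. Show the joint draws on the cost-effectiveness plane, and state how dominance will be reported.
- Keep the range-based Monte Carlo as a sensitivity analysis for unit-cost inputs without participant sampling error (labor market values, rent). State the ranges and their source, and do not call its output a confidence interval.
- Apply the same rules to the cost-utility analysis.

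The cost is SAP wording and modest extra programming. No new data are needed: participant costs, EQ-5D and weight are already collected.
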